8.1.1 Adverse Drug Reaction

All noxious and unintended responses to study drug related to any dose should be considered an adverse drug reaction (ADR).

The phrase “responses to study drug” means that a causal relationship between study drug and an AE is at least a reasonable possibility, ie, the relationship cannot be ruled out. All AEs judged by the reporting Investigator or the Sponsor as having a reasonable causal relationship to study drug qualify as ADRs.

8.1.2 Unexpected Adverse Drug Reaction

An Unexpected Adverse Drug Reaction is defined as an adverse reaction, the nature or severity of which is not consistent with the applicable product information. For razuprotafib, the reference safety information is included in the Investigator’s Brochure currently in force. The reference safety information will be reviewed yearly.

8.1.3 Assessment of Adverse Events by the Investigator

The Investigator is responsible for the detection and documentation of events meeting the criteria and definitions of an AE or SAE as described in this protocol. The Investigator will assess the severity (intensity) of each AE according to the CTCAE version 5.0, and will also categorize each AE as to its potential relationship to study drug using the categories of yes or no.

Assessment of Severity

The severity of all AEs should be graded according to the CTCAE version 5.0. For those AE terms not listed in the CTCAE, the following grading system should be used:

- CTCAE Grade 1: Mild; asymptomatic or mild symptoms; clinical or diagnostic observations only; intervention not indicated;
- CTCAE Grade 2: Moderate; minimal local or noninvasive intervention indicated; limiting age-appropriate instrumental activities of daily living;
- CTCAE Grade 3: Severe or medically significant but not immediately life-threatening; hospitalization or prolongation of hospitalization indicated; disabling; limiting self-care activities of daily living;
- CTCAE Grade 4: Life-threatening consequences; urgent intervention indicated; and
- CTCAE Grade 5: Death related to the AE.

It is important to distinguish between severe AEs and SAEs. Severity is a classification of intensity, whereas an SAE is an AE that meets serious criteria, as described in Section [8.2](#).

Causality Assessment

The relationship of an AE to the administration of the study drug is to be assessed according to the following definitions:

No (unrelated, not related, unlikely to be related) – The time course between the administration of study drug and the occurrence or worsening of the AE rules out a causal relationship and another cause (concomitant drugs, therapies, complications, etc) is suspected.

Yes (possibly, probably, or definitely related) – The time course between the administration of study drug and the occurrence or worsening of the AE is consistent with a causal relationship and no other cause (concomitant drugs, therapies, complications, etc) can be identified.

The definition implies a reasonable possibility of a causal relationship between an AE or SAE and the study drug. This means that there are facts (evidence) or arguments to suggest a causal relationship.

The following factors should also be considered:

- The temporal sequence from study drug administration;

The event should occur after the study drug is given. The length of time from study drug exposure to event should be evaluated in the clinical context of the event.

- Underlying, concomitant, intercurrent diseases;

Each report should be evaluated in the context of the natural history and course of the disease being treated and any other disease the subject may have.

- Concomitant drug;

The other drugs the subject is taking or the treatment the subject receives should be examined to determine whether any of them might be recognized to cause the event in question.

- Known response pattern for this class of study drug;

Clinical and/or preclinical data may indicate whether a particular response is likely to be a class effect.

- Exposure to physical and/or mental stresses; and

The exposure to stress might induce adverse changes in the recipient and provide a logical and better explanation for the event.

- The pharmacology and PK of the study drug.

The known pharmacologic properties (absorption, distribution, metabolism, and excretion) of the study drug should be considered.

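### Protocol 8.1.3's yes/no causality definitions leave an AE with compatible timing and another identified cause in neither category, and the Yes condition is narrower than the 8.1.1 standard

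*Protocol*

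**What the plan says.** Protocol 8.1.3 has the investigator rate each AE's relationship to study drug "using the categories of yes or no". No third category is offered. Each answer has a label and a two-part condition.

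- ***Yes*.** The label takes in events that are only possibly related. The condition is that the time course is "consistent with a causal relationship and no other cause (concomitant drugs, therapies, complications, etc) can be identified".
- ***No*.** The label takes in events that are merely unlikely to be related. The condition is that the time course "rules out a causal relationship and another cause (concomitant drugs, therapies, complications, etc) is suspected".

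The section then adds: "The definition implies a reasonable possibility of a causal relationship between an AE or SAE and the study drug". It lists six further factors to consider. On underlying disease it says: "Each report should be evaluated in the context of the natural history and course of the disease being treated". On concomitant drugs it says that they "should be examined to determine whether any of them might be recognized to cause the event in question".

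Protocol 8.1.1 defines a response to study drug differently. It means that "a causal relationship between study drug and an AE is at least a reasonable possibility, ie, the relationship cannot be ruled out". The absence of other causes is not required. Either the investigator or the Sponsor may make that judgement.

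**The concern.** The two definitions are not complements. Each joins two requirements with 'and', so an event that meets one half of each has no category. The case that matters is an event that follows a dose closely and for which the investigator can also name another cause.

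That case looks likely in this population, although this is inference. Subjects are hospitalized with COVID-19 on standard of care, and drugs such as remdesivir and dexamethasone are permitted (Protocol 5.6.2). Dosing is every 8 hours for 7 days, so an on-treatment event falls within hours of a dose. Blood pressure is a concrete example. Protocol 1.2 and 5.2 describe a dose-dependent fall as a known effect of the drug. If a low reading follows a dose and another cause is identified as well, 8.1.3 does not say how to rate it.

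Two things are at stake. Sites may resolve the gap differently. Events rated *No* whose relationship cannot in fact be ruled out would be missing from the related-AE counts by the protocol's own 8.1.1 standard.

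**Working it through.** The plan states no figure on this point, so the check is logical.

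**Step 1. Test the literal definitions.** Cross timing with other cause. The protocol uses both 'suspected' (in *No*) and 'identified' (in *Yes*) and defines neither. The table treats an other cause simply as present or absent.

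| Timing | Other cause | *Yes* condition met? | *No* condition met? | Category |
|---|---|---|---|---|
| Compatible | Absent | Yes | No | *Yes* |
| Compatible | Present | No (a cause is identified) | No (timing does not rule it out) | None |
| Ruled out | Present | No | Yes | *No* |
| Ruled out | Absent | No | No (no other cause suspected) | None literally; naturally *No* |

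Two of the four combinations are literally uncovered. The last row is harmless, because nobody would call an event related when its timing rules that out. The second row is the contested one. If an other cause is only suspected and not identified, *Yes* can still be met, so the gap concerns identified causes.

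**Step 2. Compare *Yes* with 8.1.1.** Under 8.1.1 the question is whether a relationship is a reasonable possibility, that is, whether it cannot be ruled out. An identified other cause may rule the drug out, but need not. Some second-row events therefore qualify under 8.1.1, while *Yes* in 8.1.3 excludes all of them. *Yes* is the narrower standard.

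**Step 3. Compare 8.1.3 with itself.** A label that includes possibly related events does not fit a condition that no other cause can be identified. The sentence about a reasonable possibility echoes 8.1.1 but leaves that condition in place. On the other side, a label that includes unlikely events does not fit a condition that timing rules causality out.

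**Step 4. See whether the six factors close the gap.** Three of them (disease, concomitant drugs, stress) send the investigator to look for other causes. None says which category follows when one is found.

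**Step 5. Trace where the rating is used.**

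- *Tables.* Protocol 9.2.4 summarizes AEs and SAEs by relationship. In SAP 3.6.1, one of the five AE overview categories uses relatedness directly.
- *Reporting.* Under Protocol 8.3, SAEs after Day 28 are reported only if the investigator considers them related. This route is probably small. Day 28 is about 28 − 7 = 21 days after the last dose, or at least 28 − 14 = 14 days if dosing is extended, and the half-life in earlier studies was about 1 hour (Protocol 1.2).
- *Stopping criteria.* In Protocol 4.4.1, one of four criteria turns on relatedness and another does so in one clause. In 4.4.2, one of two triggers does. Neither section cites 8.1.3 or its yes/no rating.
- *Not affected.* Neither of the two safety endpoints in Protocol 8.7 uses relatedness. All SAEs up to Day 28 are reported whatever the rating.

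**The case against.** The best reply is that 8.1.3 should be read for its purpose. The answer must be *Yes* or *No*. *No* is reserved for timing that rules causality out, which mirrors 8.1.1. *Yes* reaches possibly related events, and the sentence that follows uses the same phrase as 8.1.1. On that reading the contested event is *Yes*, just as the harmless row is naturally *No*, and the fault is loose drafting. Both 8.1.1 and the six factors also call for judgement. The factors were never meant to assign categories, and one of them accepts that stress may explain an event better.

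This reading is reasonable, and a careful investigator might adopt it. It works only by setting aside an explicit condition of *Yes*, and another careful investigator could apply that condition as written.

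The mitigations are real:

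- the second trigger in 4.4.2 applies regardless of relatedness;
- scheduled DRC reviews and ad hoc safety reviews take place;
- Protocol 4.5 allows study drug to be discontinued without a finding of relatedness;
- the Sponsor makes its own causality judgement under 8.1.1;
- all AEs are listed;
- the eCRF completion procedures mentioned in Protocol 11.4 are not in the documents and may already settle the matter.

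These limit the consequence. They do not reconcile the protocol text.

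A reader might also infer that the stopping criteria and the DRC trigger run on the 8.1.3 rating. The documents do not establish that. Sections 4.4.1 and 4.4.2 speak of relatedness in their own words, and reliance on 8.1.3 is plausible but inferred.

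**Conclusion.** The textual conflict is established. Read literally, the two definitions in 8.1.3 are not exhaustive, and the no-other-cause condition of *Yes* is narrower than 8.1.1 and at odds with 8.1.3's own label and following sentence. Confidence in this is high.

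Inconsistent coding and under-counting of related AEs are inferences from that conflict. They assume that some investigators apply the condition as written and that no site guidance overrides it. The number of events cannot be estimated, and the cell counts in the table measure wording, not effect.

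Two further readings go too far. A reader might conclude that the safety comparison between arms is biased. Investigators are blinded (Protocol 5.3), so coding should not depend on arm, and the likelier result is inconsistency between sites or under-counting in all arms. A reader might also conclude that safety reporting as a whole is compromised. The named endpoints, SAE reporting to Day 28 and the full AE listings do not depend on the rating.

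The point should be corrected because the protocol contradicts itself on a rating that feeds planned tables and some reporting, and because the repair is inexpensive.

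**What to change.** Rewrite the two definitions in Protocol 8.1.3 so that they are mutually exclusive and exhaustive. Reconcile two elements with 8.1.1, so that one stated standard governs both sections: the no-other-cause condition in *Yes*, and the conjunction in *No* that requires both excluding timing and another suspected cause. Carry the agreed wording into the eCRF guidance. For AEs already coded, either re-rate them or state the date from which the new wording applies.

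The sponsor should also confirm that the references to relatedness in 4.4.1 and 4.4.2 are consistent with the reconciled definition. No stopping or dosing rule is proposed here.

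The cost is protocol and guidance wording plus the re-rating or change date. The downside is that the number of AEs flagged as related may change in all arms.

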8.2 Serious Adverse Events/Drug Reaction

An AE or adverse reaction is considered serious if, in the view of either the Investigator or Sponsor, it results in any of the following outcomes:

- Death;

- Is life-threatening;

Note: The term “life-threatening” in the definition of “serious” refers to an event in which the subject was at immediate risk of death at the time of the event. It does not refer to an event that hypothetically might have caused death if it were more severe.

- Requires hospitalization or prolongation of existing hospitalizations;

Note: Any hospital admission with at least 1 overnight stay will be considered an inpatient hospitalization. An emergency room or urgent care visit without hospital admission will not be recorded as an SAE under this criterion, nor will hospitalization for a procedure scheduled or planned before signing of informed consent, or elective treatment of a pre-existing condition that did not worsen from baseline. However, unexpected complications and/or prolongation of hospitalization that occur during elective surgery should be recorded as AEs and assessed for

seriousness. Admission to the hospital for social or situational reasons (ie, no place to stay, live too far away to come for hospital visits, respite care) will not be considered inpatient hospitalizations.

- Results in persistent or significant disability/incapacity or substantial disruption of the ability to conduct normal life functions;
- Is a congenital anomaly/birth defect; or
- Is an important medical event.

Note: Important medical events that do not meet any of the above criteria may be considered an SAE when, based upon appropriate medical judgment, they may jeopardize the subject and may require medical or surgical intervention to prevent 1 of the outcomes listed above. Examples of such medical events include allergic bronchospasm requiring intensive treatment in an emergency room or at home, blood dyscrasias or convulsions that do not result in inpatient hospitalizations, or the development of drug dependency.

8.3 Serious Adverse Event Reporting – Procedures for Investigators

Initial Reports

All SAEs occurring from the time of the first dose of study drug until Day 28 must be reported to Medpace Clinical Safety **within 24 hours** of knowledge of the occurrence. After the reporting window, any SAE that the Investigator considers related to study drug must be reported to Medpace Clinical Safety or the Sponsor/designee.

To report the SAE, complete the SAE form electronically in the electronic data capture (EDC) system for the study. When the form is completed, Medpace Safety personnel will be notified electronically by the EDC system and will retrieve the form. If the event meets serious criteria and it is not possible to access the EDC system, send an email to Medpace Safety at [contact] or call the Medpace SAE hotline (telephone number listed below), and fax/email the completed paper SAE form to Medpace (contact information listed in Section 8.6) within 24 hours of awareness. When the EDC system becomes available, the SAE information must be entered within 24 hours of the system becoming available.

Follow-Up Reports

The Investigator must continue to follow the subject until the SAE has subsided or until the condition becomes chronic in nature, stabilizes (in the case of persistent impairment), or the subject dies.

Within 24 hours of receipt of follow-up information, the Investigator must update the SAE form electronically in the EDC system for the study and submit any supporting documentation (eg, subject discharge summary or autopsy reports) to Medpace Clinical Safety via fax or email. If it is not possible to access the EDC system, refer to the procedures outlined above for initial reporting of SAEs.

8.4 Pregnancy Reporting

If a subject becomes pregnant during the study or within the safety follow-up period defined in the protocol, the Investigator is to stop dosing with study drug immediately. The subject should

discontinue study drug but continue to complete all safety assessments at subsequent study visits up to and including Day 28, unless the subject or LAR withdraws consent or is lost to follow-up.

A pregnancy is not considered to be an AE or SAE; however, it must be reported to Medpace Clinical Safety **within 24 hours of knowledge** of the event. Medpace Clinical Safety will then provide the Investigator/site the Exposure In Utero (EIU) form for completion. The Investigator/site must complete the EIU form and fax/email it back to Medpace Clinical Safety.

If the female partner of a male subject becomes pregnant while the subject is receiving study drug or within the safety follow-up period defined in the protocol, the Investigator should notify Medpace Clinical Safety as described above.

The pregnancy should be followed until the outcome of the pregnancy, whenever possible. Once the outcome of the pregnancy is known, the EIU form should be completed and faxed/mailed to Medpace Clinical Safety. If the outcome of the pregnancy meets the criteria for immediate classification as an SAE (ie, postpartum complication, spontaneous abortion, stillbirth, neonatal death, or congenital anomaly), the Investigator should follow the procedures for reporting an SAE.

8.5 Expedited Reporting

The Sponsor/designee will report all relevant information about Suspected Unexpected Serious Adverse Reactions (SUSARs) that are fatal or life-threatening as soon as possible to the Food and Drug Administration (FDA), and in any case no later than 7 days after knowledge by the Sponsor/designee of such a case. Relevant follow-up information will subsequently be communicated within an additional 8 days.

All other SUSARs will be reported to the FDA as soon as possible but within a maximum of 15 days of first knowledge by the Sponsor/designee.

The Sponsor/designee will also report any additional expedited safety reports required in accordance with the timelines outlined in country-specific legislation.

The Sponsor/designee will also inform all Investigators as required per local regulation.

The requirements above refer to the requirements relating to investigational medicinal product.

8.6 Special Situation Reports

Special situation reports include reports of overdose, misuse, abuse, medication error, and reports of adverse reactions associated with product complaints.

- **Overdose:** Refers to the administration of a quantity of study drug given per administration or cumulatively (accidentally or intentionally), which is above the maximum recommended dose according to the protocol. Clinical judgment should always be applied. In cases of a discrepancy in the drug accountability, overdose will be established only when it is clear that the subject has taken additional dose(s) or the Investigator has reason to suspect that the subject has taken additional dose(s).
- **Misuse:** Refers to situations where study drug is intentionally and inappropriately used in a way that is not in accordance with the protocol instructions or local prescribing information and may be accompanied by harmful physical and/or psychological effects.

- **Abuse:** Is defined as persistent or sporadic, intentional excessive use of study drug, which is accompanied by harmful physical or psychological effects.
- **Medication error:** Is any unintentional error in the prescribing, dispensing, or administration of study drug by a healthcare professional, subject, or consumer, respectively. The administration or consumption of the unassigned treatment and administration of an expired product are always reportable as medication errors. Cases of subjects missing doses of study drug are not considered reportable as medication errors.
- **Product complaint:** Is defined as any written, electronic, or oral communication that alleges deficiencies related to the identity, quality, durability, reliability, safety, effectiveness, or performance of a drug or device after it is released for distribution. A Special Situations Report form will only be completed if a complaint is associated with an ADR.

All special situation events as described above must be reported on the Special Situations Report form and faxed/mailed to Medpace Clinical Safety (contact information listed below) within **24 hours of knowledge of the event**. All AEs associated with these special situation reports should be reported as AEs or SAEs as well as recorded on the AE eCRF and/or the SAE report form. Details of the symptoms and signs, clinical management, and outcome should be provided, when available.

Safety Contact Information:

Medpace Clinical Safety

Medpace SAE hotline – USA:

8.7 Safety Assessments

The safety endpoints include the following:

- Number of subjects with any SAE; and
- Number of subjects with any treatment-emergent AE.

Safety will be determined by evaluating clinical laboratory findings (blood chemistry, hematology, and coagulation), vital signs (blood pressure, heart rate, SpO₂ [for non-ventilated subjects only], and respiratory rate), 12-lead electrocardiograms, and AEs reported during the study.

8.8 Clinical Laboratory Evaluations

Samples for blood chemistry, hematology, and coagulation will be obtained as indicated in [Appendix A](#). See [Appendix B](#) for a complete list of analytes. If a blood chemistry, hematology, or coagulation assessment was performed within 24 hours prior to the first dose of study drug, it is not necessary to repeat the assessment on Day 1. Effort should be made to obtain blood chemistry, hematology, and coagulation at approximately the same time on each day indicated in [Appendix A](#); however, it should not be considered a protocol deviation if this is not possible. After the Treatment Period, blood chemistry, hematology, and coagulation will be assessed weekly until Day 28, unless discharged. All safety clinical laboratory evaluations will be performed at the local laboratory as indicated in [Appendix A](#).

A local urine pregnancy test will be performed for females of childbearing potential only at Screening.

Arterial blood gas should be obtained locally only if clinically indicated. If arterial blood gas is obtained, the subject's current oxygen requirement should also be recorded.

8.9 Vital Signs

Vital signs will be collected as indicated in [Appendix A](#). Vital signs will include blood pressure, heart rate, SpO₂ (for non-ventilated subjects only), and respiratory rate. If vital signs are to be assessed at the same time point as a blood draw, vital signs should be assessed prior to blood draw. Vital signs will be assessed within 1 hour prior to each dose of study drug and 30 (± 15) minutes, 60 (± 15) minutes, and 90 (± 15) minutes following each dose of study drug. Additionally, after the first dose of study drug, supine blood pressure will be assessed every 5 (± 1) minutes for the first 15 minutes, and then every 15 (± 5) minutes for the first hour. Subjects will be in the supine position during dosing, and they must remain supine with their head no higher than 45° until the vital sign assessment is completed 90 minutes following dosing. After the Treatment Period, vital signs will be assessed daily until Day 28, unless discharged.

Temperature will be measured at Screening only.

8.10 12-lead Electrocardiogram

12-lead electrocardiograms will be performed as indicated in [Appendix A](#). If a 12-lead electrocardiogram was performed within 24 hours prior to informed consent, it is not necessary to repeat the 12-lead electrocardiogram at Screening.

